Intracanalicular Dexamethasone used in conjunction with Restasis (cyclosporine ophthalmic emulsion) for the treatment of signs and symptoms of dry eye disease as compared to Restasis with Lotemax (loteprednol etabonate ophthalmic suspension 0.5%) and Restasis monotherapy.

[name] STUDY

Compound:

DEXTENZA® (dexamethasone ophthalmic insert) 0.4 mg for intracanalicular use

Study Name:

[name] STUDY

Protocol Number:

TC-2020-DexRes

Clinical Phase:

Open label prospective

Date of Issue:

01/11/2021

Primary Investigator:

[name]

Site Name & Location:

Cleveland Eye Clinic
[name],
[name]

[name] STUDY V2

CLINICAL STUDY PROTOCOL SYNOPSIS

TITLE	Intracanalicular Dexamethasone used in conjunction with Restasis (cyclosporine ophthalmic emulsion) for the treatment of signs and symptoms of dry eye disease as compared to Restasis with Lotemax (loteprednol etabonate ophthalmic suspension 0.5%) and Restasis monotherapy.
SITE LOCATION(S)	Cleveland Eye Clinic [name]
PRINCIPAL INVESTIGATOR	[name]
OBJECTIVE(S)	To evaluate the benefit of treatment with a physician administered intracanalicular dexamethasone insert in patients with dry eye who are beginning treatment with Restasis (cyclosporine ophthalmic emulsion) to reduce the signs and symptoms of dry eye disease.
STUDY DESIGN	Prospective Open-label Interventional Study
STUDY DURATION	6 months including screening and enrollment
ESTIMATED STUDY COMPLETION DATE	3 months after date of insertion
POPULATION	
Sample Size:	30 patients (60 eyes)
Target Population:	Patients with dry eye who are about to begin treatment with Restasis bilaterally to reduce the signs and symptoms of dry eye disease and who have not been on topical immunomodulation for a minimum of 3 months prior to the start of the study.
TREATMENT(S)	

[name] STUDY V2

Study Drug	Sustained Release Dexamethasone, 0.4 mg
Dose/Route/Schedule:	All patients will be prescribed Restasis BID for both eyes who have not been on topical immunomodulation for a minimum of 3 months, and who would benefit from addition of topical pharmacotherapy (immunomodulation). There will be 3 groups. 10 patients will receive Restasis BID and Dextenza in both eyes, 10 patients will receive Restasis BID for 12 weeks and Lotemax BID for one month in both eyes and 10 patients will receive Restasis BID monotherapy.

Screening/ Prescription

- 1-week
- 2-week
- 1 month
- 2 month
- 3 month

ENDPOINT(s)

PRIMARY:

- Mean change in ocular surface staining (sodium fluorescein and lissamine green) from baseline at week 1, week 2, week 4, week 8, and week 12 as measured by the NEI grading scale

Secondary:

- Mean change in MMP-9 from baseline at week 1, week 2, week 4, week 8 and week 12 as measured by InflammaDry
- Mean change in tear break-up time (TBUT) from baseline at week 1, week 2, week 4, week 8 and week 12
- Mean change in conjunctival injection from baseline at week 1, week 2, week 4, week 8 and week 12 as measured on a scale of 0-4 and graded by the physician
- Change from baseline in meibomian gland scores (expressibility with MGE) at week 1, week 2, week 4, week 8 and week 12.
- Mean change in tear osmolarity from baseline at week 1, week 2, week 4, week 8 and week 12 as measured by Tear Lab
- Mean change in SPEED scores from baseline at week 1, week 2, week 4, week 8 and week 12
- Mean change in Best-corrected Visual Acuity (BCVA) from baseline at week 1, week 2, week 4, week 8 and week 12 as measured by ETDRS chart
- Mean change in Schirmer's score from baseline at week 1, week 2, week 4, week 8 and week 12 as measured by Schirmer's test strip

TABLE OF CONTENTS

List of Tables	6
1. Introduction and Rationale	7
1.1. Introduction	7
1.2. Rationale	7

1. INTRODUCTION AND RATIONALE

1.1. Introduction

Dry eye disease (DED) is a multifactorial disorder of the ocular surface that severely impacts vision and quality of life. Risk factors that contribute to DED include age, gender, hormones, autoimmune disorders, local environment, use of video displays, contact lens wear and exposure to medications/preservatives, all potentially leading to secretory or evaporative DED, or both.¹ The Tear Film and Ocular Surface Society's Dry Eye Workshop II definition recognizes the impact of inflammation, saying, "Dry eye is a multifactorial disease of the ocular surface characterized by a loss of homeostasis of the tear film, and accompanied by ocular symptoms, in which tear film instability and hyperosmolarity, ocular surface inflammation and damage, and neurosensory abnormalities play etiological roles."²

Topical cyclosporine A (Restasis) is indicated to increase tear production in patients whose tear production is presumed to be suppressed because of ocular inflammation associated with DES. A significant number of studies are available concerning the use of cyclosporine as a way to modulate inflammation. Positive effects are consistently seen with the use of this drug for treatment of DES.³ Topical application exerts a therapeutic effect without causing systemic side effects, because only small amounts can penetrate into the bloodstream after topical application.⁴

After determining the severity of the inflammation in a DED patient, the doctor can then decide if a topical steroid is needed to quickly decrease the overall inflammation along with Restasis.

1.2. Rationale

Although Restasis works as an anti-inflammatory, by preventing T-cells from releasing cytokines and increases tear production in patients whose tear production is presumed to be suppressed due to ocular inflammation associated with keratoconjunctivitis sicca, we hypothesize that the addition of DEXTENZA® will provide greater symptomatic improvement than pharmacotherapy alone. Additionally, we hypothesize that the addition of DEXTENZA® will show non inferiority in comparison to Restasis in combination with Lotemax.

This study will compare and evaluate the benefit of treatment with a physician administered intracanalicular dexamethasone insert (0.4 mg) bilaterally, compared to Lotemax prescribed ~~BID~~, in patients that are prescribed Restasis bilaterally to increase tear production in patients with aqueous deficient DED. In addition, the study will evaluate physician assessment of ease of DEXTENZA® insertion.

Drug delivery platforms are an innovative exciting advancement in ophthalmology. They allow patients to eliminate topical medications which are generally associated with lack of compliance, difficulty of use and requiring help from family members. At times, patients may have to take several drops, increasing the likelihood of non-compliance and adding a level of complexity to their drop regimen.

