2. STUDY OBJECTIVES

2.1. Primary Objective

- Mean change in ocular surface staining (sodium fluorescein and lissamine green) from baseline at week 1, week 2, week 4, week 8 and week 12 as measured by the NEI grading scale

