2.2. Secondary Objectives

- Mean change in MMP-9 from baseline at week 1, week 2, week 4, week 8 and week 12 as measured by InflammaDry
- Mean change in tear break-up time (TBUT) from baseline at week 1, week 2, week 4, week 8 and week 12
- Mean change in conjunctival injection from baseline at week 1, week 2, week 4, week 8 and week 12 as measured on a scale of 0-4 and graded by the physician
- Change from baseline in meibomian gland scores (expressibility and quality) at week 1, week 2, week 4, week 8 and week 12.
- Mean change in tear osmolarity from baseline at week 1, week 2, week 4, week 8 and week 12 as measured by Tear Lab
- Mean change in DEQ-5 from baseline at week 1, week 2, week 4, week 8 and week 12
- Mean change in Best-corrected Visual Acuity (BCVA) from baseline at week 1, week 2, week 4, week 8 and week 12 as measured by ETDRS chart
- Mean change in Schirmer's score from baseline at week 1, week 2, week 4, week 8 and week 12 as measured by Schirmer's test strip

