### **Main Outcome Measures**

The primary outcome measure was the mean change in corneal surface staining (guided by use of fluorescein and lissamine green) at weeks 1, 2, 4, 8 and 12 based on the NEI grading scale. Corneal fluorescein staining was graded from 0 to 3 (none to heavy) in five regions of the cornea and summed for a total score.

All secondary outcome measures followed the same timeline with comparison at weeks 1, 2, 4, 8 and 12 in comparison to baseline. Secondary outcome measures included the mean change in tear break-up time (TBUT), the mean change in conjunctival staining (graded 0-3 in 6 regions), the mean change in tear osmolarity as measured by TearLab, the mean change in DEQ-5, the mean change in meibomian gland scores as measured by quality of meibum expression, the mean change in best-corrected distance visual acuity (BCDVA) as measured by ETDRS chart and the mean change in Schirmer's score as measured by a Schirmer's test strip.

Meibomian gland scoring involved grading the quality of expression (0-3) from 15 glands along the lower eyelid including temporal, central and nasal. For scoring, 3 was representative of clear, liquid secretions and 0 was no secretions. The DEQ-5 Dry Eye Questionnaire was used to evaluate symptoms and characterize severity of discomfort, dryness and tearing. Possible scores ranged from 0 to 22 with higher scores representing worse symptoms.

On the screening visit and the initiation of therapy including implantation of the dexamethasone insert in the study group, a physician ease of insertion questionnaire was also completed by the physician implanting the device. All device-related complications were recorded. All subject-reported adverse events were recorded at each study visit.

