## **RESULTS**

### **Patient Demographics**

Sixty eyes of 30 subjects were successfully enrolled into the study including 20 eyes of 10 subjects in the dexamethasone/cyclosporine group, 22 eyes of 11 subjects in the loteprednol/cyclosporine group and 18 eyes of 9 subjects in the cyclosporine monotherapy group. All 3 groups were summarized by baseline characteristics, which are shown in Table 2.

None of the three groups, including the study and two control groups met the primary endpoint. In the dextenza group, the mean baseline corneal staining score was  $0.5 \pm 1.0$  with 70% ( $n=14$ ) without evidence of corneal staining at baseline. The mean score at weeks 4, 8 and 12 was  $0.6 \pm 1.0$  ( $P = 0.99$ ),  $0.5 \pm 1.1$  ( $P = 0.99$ ) and  $0.7 \pm 1.4$  ( $P = 0.97$ ), respectively. In the loteprednol group, the mean baseline corneal staining score was  $0.8 \pm 1.5$  with 64% ( $n=14$ ) without corneal staining at baseline. At weeks 4, 8 and 12, the mean score was  $0.9 \pm 0.9$  ( $P = 0.99$ ),  $0.0 \pm 0.0$  ( $P = 0.06$ ) and  $0.6 \pm 1.0$  ( $P = 0.78$ ), respectively. In the cyclosporine monotherapy group, the mean baseline corneal staining score was  $0.5 \pm 0.5$  with 50% ( $n=9$ ) of eyes absent of any corneal staining at baseline. There was no significant change in corneal staining at any time point with a mean score of  $1.1 \pm 1.4$  ( $P = 0.26$ ),  $0.3 \pm 0.6$  ( $P = 0.63$ ) and  $0.5 \pm 0.7$  ( $P = 0.99$ ) at weeks 4, 8 and 12, respectively. These results, in addition to comparisons of other outcome measures, are summarized in Table 3.

There was no significant change in conjunctival staining, Schirmer scores, TBUT, tear osmolarity or meibomian gland scores at any of the follow-up time points in comparison to baseline in all three groups. These results are summarized and also demonstrated in Table 3.

Across all visits, the mean IOP remained stable in all three groups. In the cyclosporine monotherapy group, there were no instances of IOP elevation  $>10$  mmHg above baseline. Similarly, in the dextenza and loteprednol groups, there were no instances of IOP elevation  $>10$

mmHg above baseline at any time point. There were no canalicular-related complications or adverse events related to implantation of the dexamethasone insert. No patients required removal of the insert.

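### The only superiority hypothesis concerns symptoms, but the primary endpoint is a sign and every planned comparison is within-group, so no planned analysis tests that hypothesis.

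*Protocol*

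**What the plan says.** **Hypotheses.** Protocol section 1.2 gives two. The first is superiority on symptoms: "the addition of DEXTENZA® will provide greater symptomatic improvement than pharmacotherapy alone". The second is non-inferiority: "we hypothesize that the addition of DEXTENZA® will show non inferiority in comparison to Restasis in combination with Lotemax". The second names neither an endpoint nor a margin.

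**Objective.** The synopsis objective is broader. It concerns the benefit of the insert "in patients with dry eye who are beginning treatment with Restasis (cyclosporine ophthalmic emulsion) to reduce the signs and symptoms of dry eye disease".

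**Primary endpoint.** Section 2.1 has one entry: "Mean change in ocular surface staining (sodium fluorescein and lissamine green) from baseline", at five visits on the NEI scale. In the SAP (Main Outcome Measures) this becomes corneal staining: "The primary outcome measure was the mean change in corneal surface staining".

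**Symptom endpoint.** Symptoms are secondary throughout. Section 2.2 has "Mean change in DEQ-5 from baseline at week 1" and later visits, but the synopsis has "Mean change in SPEED scores from baseline at week 1" in that place. Table 1 schedules DEQ-5 at all six visits. Appendix VII lists visits 1, 3, 4, 5, 6 and 7, which leaves out visit 2 and names a visit that does not exist.

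**Analysis.** The SAP's Statistical Analysis section describes repeated measures analysis of variance within each group, then Bonferroni-corrected comparisons of each time point with baseline. It describes no comparison between groups.

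**Reported result.** "None of the three groups, including the study and two control groups met the primary endpoint".

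**The concern.** The hypothesis has two parts: a variable (symptoms) and a contrast (insert plus Restasis against treatment without the insert). The primary endpoint departs from the variable, and the analysis departs from the contrast. Someone who follows the plan exactly finishes without an estimate of the quantity in section 1.2.

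This affects how the results are read. The headline verdict is on staining. The symptom results come as separate within-group P values, which invite an informal comparison. At week 12 the insert group's DEQ-5 change was not significant (P = 0.20), while the loteprednol and monotherapy groups each had P < 0.01. A difference in significance between groups is not a test of the difference between them. The SAP Discussion then takes symptom improvement with a corticosteroid plus cyclosporine as agreeing with earlier work. It does not mention there that cyclosporine alone also improved at weeks 8 and 12. Only a between-arm contrast can show whether the insert added anything, and none is given.

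**Working it through.** The documents give no power calculation or between-arm figure, so there is nothing of the plan's own to reproduce. The check has three steps.

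**1. Match of hypothesis, endpoint and analysis**

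| Element | Variable | Contrast |
|---|---|---|
| Superiority hypothesis (1.2) | symptoms | insert + Restasis vs pharmacotherapy alone, read here as Restasis alone |
| Primary endpoint (2.1) | staining | none stated |
| Secondary symptom endpoint (2.2) | DEQ-5 (SPEED in the synopsis) | none stated |
| SAP analysis | all outcomes | each group vs its own baseline |

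No row below the first has both the variable and the contrast of the hypothesis.

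**2. The missing contrast, from reported summaries**

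Inputs are from the SAP results, DEQ-5 mean ± SD. Group sizes are patients enrolled (10 and 9), because DEQ-5 is a patient-level score. Numbers observed at each visit are not given, so full attendance is assumed.

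| | Baseline | Week 4 | Week 8 | Week 12 |
|---|---|---|---|---|
| Insert, n = 10 | 14.1 ± 4.0 | 10.6 ± 4.6 | 11.3 ± 4.5 | 10.3 ± 6.3 |
| Monotherapy, n = 9 | 14.4 ± 3.7 | 12.2 ± 2.2 | 10.6 ± 2.6 | 9.4 ± 3.1 |
| Insert change | | -3.5 | -2.8 | -3.8 |
| Monotherapy change | | -2.2 | -3.8 | -5.0 |
| Difference in change | | -1.3 | +1.0 | +1.2 |

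Higher DEQ-5 is worse, so a negative difference favours the insert.

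Change SDs are not reported, so follow-up SDs stand in: SE = sqrt(s1²/10 + s2²/9), with Welch degrees of freedom.

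- Week 4: sqrt(4.6²/10 + 2.2²/9) = 1.63; half-width 2.16 × 1.63 = 3.5; interval -4.8 to +2.2.
- Week 8: sqrt(4.5²/10 + 2.6²/9) = 1.67; half-width 2.14 × 1.67 = 3.6; interval -2.6 to +4.6.
- Week 12: sqrt(6.3²/10 + 3.1²/9) = 2.24; half-width 2.15 × 2.24 = 4.8; interval -3.6 to +6.0.

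*Sensitivity to the stand-in.* With an assumed baseline to follow-up correlation r, the change SD is sqrt(s0² + s1² - 2·r·s0·s1). At week 12 and r = 0.5:

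- insert: sqrt(16 + 39.69 - 25.2) = 5.5
- monotherapy: sqrt(13.69 + 9.61 - 11.47) = 3.4

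The same steps at each visit give these half-widths:

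| Assumed r | Week 4 | Week 8 | Week 12 |
|---|---|---|---|
| 0 | 5.1 | 5.1 | 6.1 |
| 0.5 | 3.7 | 3.7 | 4.4 |
| 0.8 | 2.5 | 2.4 | 3.1 |

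Zero lies inside the interval at every visit, even at r = 0.8.

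**3. What a DEQ-5 comparison of this size could detect**

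Assume two-sided 0.05, 80% power and 10 patients per arm. The detectable difference is (1.960 + 0.842) × SD × sqrt(2/10) = 1.253 × SD. At SDs reported for these two arms this is 4.6 points (SD 3.7), 5.0 (SD 4.0) and 7.9 (SD 6.3).

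**The case against.** **A sign is a legitimate primary here.** The study title and synopsis objective cover signs and symptoms, and section 3.1 speaks only of benefit in managing dry eye disease. A reader might infer that the primary result says nothing about what the trial set out to show. The documents do not support that, because staining addresses the signs half of the stated objective. The non-inferiority hypothesis names no endpoint, so it cannot be ruled out that it was meant to attach to staining. This stands, and it limits the point to the superiority hypothesis.

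**The report does not present the staining verdict as a symptom verdict.** The SAP Discussion says that the unmet primary endpoint was improvement in corneal staining, symptoms are reported separately, and efficacy is called unclear. This also stands. What the report lacks is the between-arm symptom estimate.

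**Changing the primary would not have helped much.** Reassigning the variable alone leaves the within-group analysis in place. Even with the right contrast, differences below about 4.6 points would probably be missed. A patient-reported primary in an open-label study is also exposed to expectation bias, so preferring an investigator-graded sign is arguable. With results known, promoting DEQ-5 now would raise a secondary endpoint above the prespecified primary. These arguments count against replacing the primary. They do not count against reporting the missing contrast under a post hoc label.

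**Conclusion.** The point holds in this form. Section 1.2 makes a superiority claim about symptoms, the primary endpoint is staining, and no planned analysis compares arms. The primary result bears on the signs part of the objective and leaves the superiority hypothesis untested.

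On the reported means, the difference in DEQ-5 change is -1.3, +1.0 and +1.2 points, with approximate half-widths of 3.5, 3.6 and 4.8. The symptom hypothesis is neither supported nor excluded. A reader might infer from the sign change after week 4, or from the pattern of within-group P values, that the insert did worse than Restasis alone. Differences of about one point against these half-widths do not support that.

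The result rests on three assumptions: follow-up SDs (or the assumed correlations) in place of change SDs, all enrolled patients contributing at each visit, and pharmacotherapy alone meaning Restasis alone. Any causal reading also depends on how groups were formed, and the documents conflict. Protocol section 3.1 says non-randomized, whereas the SAP (Patients and Discussion) says randomized.

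**What to change.** 1. Keep staining as the prespecified primary endpoint, with its verdict as reported.
2. Add a patient-level, between-arm comparison of DEQ-5 change, insert plus Restasis versus Restasis alone, at one stated visit with a 95% interval from the patient data. Label it a post hoc test of the section 1.2 hypothesis. Give the reason for the visit chosen and show the other reported visits beside it, since the results are already known. The questionnaire asks about the past month, so at weeks 1 and 2 it reaches back before treatment.
3. State that the symptom hypothesis is neither supported nor excluded, if the patient-level interval agrees with the approximate one here.
4. Reconcile the symptom instrument (SPEED in the synopsis, DEQ-5 in section 2.2), the DEQ-5 visit list in Appendix VII with Table 1, and the statements on randomization.

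**Cost.** A short analysis of data already collected, and text corrections. The added estimate will be post hoc, imprecise and exposed to expectation bias because the study is open-label, and the report should say so beside it.

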1.2.1. Rationale for Study Design

This prospective study will use a head to head design for 30 participants, 60 eyes. All eyes will receive bilateral Restasis. The study group will consist of 20 eyes receiving DEXTENZA® insertion. The control groups will consist of 20 eyes receiving Lotemax and 20 eyes will have Restasis monotherapy.

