3. STUDY DESIGN

3.1. Study Description and Duration

This prospective, open-label, single-center, non-randomized, investigator-sponsored clinical study seeks to investigate the benefit of managing patients with DED with a sustained release intracanalicular dexamethasone (0.4 mg) insert in addition to Restasis compared to Restasis in conjunction with Lotemax and Restasis alone. In addition, this study will evaluate the ease of DEXTENZA® insertion.

After screening a given patient for inclusion and exclusion criteria, and gaining informed consent, both eyes will be prescribed Restasis. Both eyes of 10 patients will be selected to receive DEXTENZA® insertion (study group), while 10 patients will be prescribed Lotemax and 10 patients will be on Restasis monotherapy (control groups). Per patient, the study period will last for approximately 12 weeks after the DEXTENZA® insertion, consisting of one screening/prescription visit and 5 post-procedure follow-up visits (week 1, week 2, week 4, week 8 and week 12). At week 1, week 2, week 4, week 8 and week 12, primary and secondary endpoints will be assessed alongside standard-of-care procedures. Adjusting for enrollment period, the study will last a total of approximately 9 months.

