Prior studies have demonstrated the favorable use of topical corticosteroids as an induction agent in combination with topical cyclosporine to augment the anti-inflammatory properties offered by cyclosporine. Although both the topical steroid and intracanalicular dexamethasone groups in this present study offered similar results, there are considerations unique to corticosteroids as it relates to sustained drug delivery. The sustained-release insert described herein offers theoretical benefits to bypass the challenges and potential side effects of topical corticosteroids. Topical agents, which are instilled intermittently, inevitably lead to variability in drug concentration owing to the poor bioavailability of the agent. The insert's intracanalicular location, with close proximity to the ocular surface, purports to offer a superior bioavailability profile with improved consistency of drug concentration in contrast to topical administration. The tapered delivery of drug from the insert over the course of 30 days minimizes the risk for rebound inflammation, which can occur with abrupt discontinuation of topical steroids. In addition, the preservative-free composition of the insert overcomes concerns related to preservatives and ocular surface toxicity, an established issue related to long-term use of topical drops.

This study has a number of limitations. The sample size was small in each group. The primary endpoint, which was improvement in corneal staining, was not met by any of the three groups. However, it is important to note that corneal staining was not a component of the inclusion criteria and thus future studies with refined inclusion criteria would be beneficial to evaluate the value of dexamethasone combined with cyclosporine 0.05% in improving corneal staining. Further, it's possible that an increase in sample size and an adequately powered study could lead to meaningful changes in other parameters such as TBUT and Schirmer scores, both of which have been demonstrated to improve following use of cyclosporine 0.05% in prior studies.

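### Non-inferiority to Restasis plus Lotemax is not tied to evidence that either steroid adds to Restasis, so a reading of similar efficacy cannot be told apart from no added effect of either

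*Protocol*

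**What the plan says.** Protocol section 1.2 (Rationale) sets out two hypotheses side by side. The first is that "we hypothesize that the addition of DEXTENZA® will provide greater symptomatic improvement than pharmacotherapy alone". The second is that "we hypothesize that the addition of DEXTENZA® will show non inferiority in comparison to Restasis in combination with Lotemax". Neither is made conditional on the other. The second has no margin, endpoint, visit or confidence level, and it does not reappear among the objectives in section 2.

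Section 1.2.1 provides both comparators: "The control groups will consist of 20 eyes receiving Lotemax and 20 eyes will have Restasis monotherapy". The SAP reports that 10 patients received the insert, with "22 eyes of 11 subjects in the loteprednol/cyclosporine group and 18 eyes of 9 subjects in the cyclosporine monotherapy group".

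The protocol has no statistical section. The SAP's Statistical Analysis section describes a repeated measures ANOVA within each group and Bonferroni-corrected comparisons of each visit with baseline. It describes no comparison between arms. The SAP Discussion then says: "Although both the topical steroid and intracanalicular dexamethasone groups in this present study offered similar results". The SAP Conclusion suggests that the insert may improve delivery with no loss of safety or efficacy.

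**The concern.** On a shared Restasis background, non-inferiority to Restasis plus Lotemax carries information about the insert only if Lotemax itself adds something at the endpoint and visit in question. If it adds nothing there, an insert with no effect is truly no worse than Lotemax, and a result of no difference is what one would expect.

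Two conclusions are therefore open whenever the steroid arms look alike: the insert works about as well as Lotemax, or neither adds to Restasis. The monotherapy arm can separate them, but neither document uses it for that. Supplying a margin and an insert-versus-Lotemax test would not close the gap. At stake is what may be claimed for the insert as a substitute for topical steroid.

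**Working it through.** **Inputs.** DEQ-5 means and SDs come from the SAP results text (higher is worse). Patient numbers are 10 (insert), 11 (Lotemax) and 9 (monotherapy). I assume that every enrolled patient contributed at each visit.

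| Arm | Baseline | Week 4 | Week 8 | Week 12 |
|---|---|---|---|---|
| Insert | 14.1 (4.0) | 10.6 (4.6) | 11.3 (4.5) | 10.3 (6.3) |
| Lotemax | 14.4 (2.4) | 11.0 (2.4) | 9.1 (4.0) | 10.2 (3.8) |
| Monotherapy | 14.4 (3.7) | 12.2 (2.2) | 10.6 (2.6) | 9.4 (3.1) |

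**Step 1: change from baseline** (visit mean minus baseline mean).

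- Insert: -3.5, -2.8, -3.8
- Lotemax: -3.4, -5.3, -4.2
- Monotherapy: -2.2, -3.8, -5.0

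**Step 2: differences in change** (negative favours the first-named arm).

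| Contrast | Week 4 | Week 8 | Week 12 |
|---|---|---|---|
| Lotemax - monotherapy | -1.2 | -1.5 | +0.8 |
| Insert - monotherapy | -1.3 | +1.0 | +1.2 |
| Insert - Lotemax | -0.1 | +2.5 | +0.4 |

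**Step 3: precision of Lotemax minus monotherapy.** The documents give no SD of change. With follow-up SDs in its place, half-width = t × sqrt(s1²/11 + s2²/9), with t = 2.101 on 18 df:

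- Week 4: 2.101 × sqrt(2.4²/11 + 2.2²/9) = 2.101 × 1.030 = 2.2
- Week 8: 2.101 × sqrt(4.0²/11 + 2.6²/9) = 2.101 × 1.485 = 3.1
- Week 12: 2.101 × sqrt(3.8²/11 + 3.1²/9) = 2.101 × 1.543 = 3.2

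Alternatively, take the variance of change as s0² + s1² - 2r·s0·s1, with an assumed correlation r between baseline and visit:

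| Lotemax - monotherapy | r = 0.5 | r = 0 |
|---|---|---|
| Week 4 | -3.9 to 1.5 | -4.9 to 2.5 |
| Week 8 | -4.7 to 1.7 | -5.8 to 2.8 |
| Week 12 | -2.4 to 4.0 | -3.6 to 5.2 |

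The half-widths are about 2.7 to 3.2 at r = 0.5 and 3.7 to 4.4 at r = 0. Every interval includes 0, and each also includes a Lotemax benefit of 2 points.

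**Step 4: the other contrasts at week 4.** Insert minus monotherapy at r = 0.5 has SE = sqrt(18.76/10 + 10.39/9) = 1.741. With t = 2.110 on 17 df the interval is -1.3 ± 3.7, or -5.0 to 2.4. Insert minus Lotemax is -0.1, with interval -3.3 to 3.1. The steroid arms are nearly identical in mean at this visit, yet neither is distinguished from monotherapy.

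**Step 5: how often an insert with no effect would pass a non-inferiority test.** Assume that Lotemax also adds nothing, with 10 patients per arm and a one-sided 2.5% level. The documents give no margin, so these margins are illustrative. The noncentral t, with noncentrality margin/(SD × sqrt(2/10)), gives:

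| Margin | SD 3 | SD 4 | SD 5 |
|---|---|---|---|
| 3 points | 56% | 35% | 25% |
| 4 points | 80% | 56% | 39% |

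In simulation, at SDs of 4 and 5 and margins of 2 to 5 points, also requiring Lotemax to beat monotherapy (one-sided 2.5%) cut these passes to 1.0% or less.

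**Step 6: power of the check.** For a true Lotemax benefit of 2 points at SD 4, the noncentrality is 2/(4 × sqrt(0.2)) = 1.12. Power is 18% with a two-arm variance and about 19% when variance is pooled over three arms. The difference detectable with 80% power is about 4 × sqrt(0.2) × (1.96 + 0.84) = 5.0 points.

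**The case against.** Several counter-arguments have force.

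- **No formal rule exists to be passed.** Non-inferiority appears once, in a rationale sentence, with no margin or test, and the SAP never claims it. This stands. A reader might infer that an ineffective insert would be declared non-inferior by construction. The documents do not support that: there is no decision rule, and under the assumed 3-point margin such an insert would still fail in 44% to 75% of trials.
- **The first hypothesis already guards against an ineffective insert.** It would if it were tested against the monotherapy arm and made a precondition. It is stated in parallel, concerns symptoms only, and has no between-arm test in the SAP.
- **Week 12 looks like evidence that Lotemax adds nothing.** A reader might infer this from the +0.8 difference. The protocol synopsis and visit procedures prescribe Lotemax for one month, so week 12 falls about eight weeks after the course ends. The interval also includes a 2-point Lotemax benefit. At weeks 4 and 8 the point estimates favour Lotemax, and no week 1 or 2 DEQ-5 values are given.
- **A strict gate is close to unattainable.** Suppose Lotemax must beat monotherapy and the margin is half the observed benefit. At SD 4 and 10 patients per arm, success is then about 1%, 4% and 10% when both steroids truly add 2, 3 or 4 points. This is a good reason to report intervals and limit the claim instead of imposing such a test.
- **The SAP is already cautious.** Its Discussion calls this a pilot with unclear efficacy and notes the small sample, and its Conclusion asks for further study. None of this tells the reader that similarity was never checked against monotherapy.

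**Conclusion.** The point holds as a limit on interpretation. The plan ties non-inferiority to no evidence of a steroid effect and describes no between-arm comparison, so similar results in the two steroid arms cannot be separated from no added effect of either. The reported DEQ-5 differences of -1.2, -1.5 and +0.8 leave both readings open.

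This does not show that Lotemax or the insert is ineffective. With 9 to 11 patients per arm, the intervals reflect lack of information.

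The logic needs no numerical assumption. The interval widths rest on substitute SDs or assumed correlations, and on the patient as the unit. The pass rates rest on assumed margins and SDs. Allocation adds a further limit: the protocol describes "This prospective, open-label, single-center, non-randomized, investigator-sponsored clinical study", while the SAP says that patients were randomized. Without randomization, every between-arm contrast here may be confounded.

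**What to change.** 1. In Protocol section 1.2 and the SAP's Statistical Analysis section, name one endpoint and one visit within the steroid treatment period for the between-arm comparison. For DEQ-5, week 4 is the only such visit with reported values.
2. Report Lotemax versus monotherapy, insert versus monotherapy and insert versus Lotemax as patient-level differences in change, each with a 95% confidence interval.
3. Allow a statement of non-inferiority or comparable efficacy only if a steroid benefit over monotherapy is shown in this trial. A non-inferiority statement would also need a justified margin.
4. Otherwise give the insert-Lotemax difference with its interval and state that non-inferiority is not assessable. Qualify the similarity statement in the SAP Discussion and the no-loss-of-efficacy suggestion in the Conclusion.
5. Label the contrasts post hoc, because results are already reported.

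The cost is some wording and three contrasts on arms already enrolled. The price in claims is higher: power is about 19% for a 2-point benefit at SD 4, so the likely outcome is inconclusive. A usable non-inferiority test would need a larger trial.
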